1. OVERALL SYNOPSIS OF THE CLINICAL INVESTIGATION

Title:	A Multi-Institutional Pilot Study of Prophylactic Cranial Tumor-Treating Fields for Patients with Extensive-stage Small Cell Lung Cancer
Device:	NovoTTF-200A System (200kHz output frequency)
Study Objectives:	To test the feasibility and compliance of TTF therapy to the brain in patients with extensive-stage small cell lung cancer with no evidence of brain metastasis. Secondary endpoints include overall survival, development of brain metastases, neurocognitive function, and QOL outcomes.
Study Design:	Prospective open label pilot study
Study Hypothesis:	The hypothesis of this study is that NovoTTF-200A will reduce the risk of developing brain metastases for ES-SCLC patients.
Sample Size:	25 patients treated with NovoTTF-200A
Study Population:	Patients with histologically proven small cell lung cancer who have undergone at least four cycles of first-line chemotherapy with a partial or complete response, above 22 years of age, no evidence of intracranial metastasis.
Primary Endpoint:	Feasibility, as measured by tolerability of TTFs (% patients continuing TTF therapy until intracranial tumor progression, discontinuation due to DLT, or 6 months).
Secondary Endpoints:	
 • Time to intracranial failure • Overall survival • Rates of intracranial failure at 2, 4, 6, 8, 10, 12 months after NovoTTF-200A • Intracranial failure free survival • Rate of decline in HVLt-R free recall, delayed recall and delayed recognition, COWAT and TMT Parts A and B at 2, 4, 6, 8, 10, 12 months after NovoTTF-200A • Time to neurocognitive failure • Neurocognitive failure-free survival • Quality of Life using the EORTC QLQ C30 with BN20 addendum • Adverse events, severity and frequency based on CTCAE V5.0
Sponsor:	[name], Vanderbilt University Medical Center

STUDY SCHEMA

2. IDENTIFICATION AND DESCRIPTION OF THE INVESTIGATIONAL DEVICE

a) Description of the Investigational Device and its Intended Purpose

The NovoTTF-200A System is an investigational medical device for the prophylactic cranial treatment of ES-SCLC patients with no evidence of brain metastases. It is intended to be used exclusively by patients in a clinical trial.

The device is a portable, battery operated system which delivers TTFIELDS to the patient by means of insulated Transducer Arrays (INE transducer arrays). NovoTTF-200A produces electric forces intended to disrupt cancer cell division.

b) Details Concerning the Manufacturer of the Investigational Device

The NovoTTF-200A System is manufactured by Novocure Ltd., [name]. Novocure Ltd. is a 21CFR820 compliant medical device company developing electric field based therapy for cancer patients. Novocure's headquarters are located in Israel. Novocure GmbH is a 21CFR820 compliant Novocure Ltd global distribution center. Novocure GmbH is based in Switzerland.

c) System Parts and Their Identification

The NovoTTF-200A System is composed of several parts, which are shown in the picture below.

1. Electric Field Generator (the device)
2. Portable Batteries
3. Charger for Portable Batteries
4. Plug In Power Supply
5. Connection Cable and Box (CAD)
6. Transducer Arrays
7. Power Cords
8. Shoulder Bag and Strap
9. Portable Battery Case

d) Traceability

All parts of the NovoTTF-200A System are identified by a unique and personal serial number. Transducer arrays are identified by lot number. Novocure maintains traceability of all parts through paper documentation and SAP ERP:

Steps	Traceability ensured by
Manufacturing	ENISO13485 Vendor Quality System
Receiving	SOP-USOC-002 Incoming Inspection and SAP ERP
Storage	SOP-USOC-004 Stockroom and SAP ERP
Shipping	SOP-USOC-003 Shipping- Final release and SAP ERP
Use	SAP ERP

e) Intended Purpose of the Investigational Device in the Proposed Clinical Investigation

[figure not shown]
[figure not shown]
The NovoTTF-200A System is intended to test the feasibility and compliance of TTF therapy to the brain in patients with extensive-stage small cell lung cancer with no evidence of brain metastasis. Secondary endpoints include overall survival, development of brain metastases, neurocognitive function, and QOL outcomes.

f) The Populations and Indications for Which the Investigational Device is Intended

Patients with histologically proven small cell lung cancer who have undergone at least four cycles of first-line chemotherapy with a partial or complete response, above 22 years of age, no evidence of intracranial metastasis.

g) Materials That Will Be in Contact with Tissues

The INE transducer arrays are applied directly to the skin.

These arrays are sterile single use devices and incorporate the following:

Part Name	Functions
1 Cover tape	Provides adhesion of the array to patients' skin
2 INE transducer array	The array delivers the treatment to the patient and measures the temperature
3 Conductive gel layers and Ceramic discs (beneath)	Gel: Ensures electric contact between the transducer array and the skin Ceramic disc: Used for the TTFields transmission
4 Mid-pads	Mechanically stabilizes the gel over the array
5 Overlapping liner	Covers the gel and the cover tape
6 Applied part cable with black connector or white connector	Connects the transducer array to the connection box

h) Training and Specific Medical or Surgical Procedures Involved in the Use of the Investigational Device

The NovoTTF-200A System is easy to use and a simple training by the Device Support Specialist (DSS) is sufficient for patients and the study team to apply the investigational device according to its intended use. No specific medical/surgical procedures are needed for the use of the investigational device.

3. JUSTIFICATION FOR THE DESIGN OF THE CLINICAL INVESTIGATIONAL PLAN

a) Prophylactic Cranial Treatment for ES-SCLC patients

Small cell lung cancer (SCLC) is a neuroendocrine tumor which encompasses approximately 15% of all lung cancers. The majority of patients present with extensive stage disease, which includes patients with bulky disease, extensive nodal involvement, and/or distant metastases. Patients with extensive-stage small cell lung cancer (ES-SCLC) have disease that is too large to treat with definitive chemoradiation, and are thus initially treated with systemic chemotherapy alone.

Metastases from SCLC have a predilection for the brain, with up to 24% of SCLC patients presenting with brain metastases at time of diagnosis [1]. Furthermore, up to 50% of patients who present with no evidence of brain metastasis at diagnosis will ultimately develop intracranial metastatic disease [2]–[4]. This high incidence of brain metastases is likely due to the low permeability of the blood-brain barrier to

systemic therapies and existence of subclinical intracranial disease at time of diagnosis. Prophylactic cranial irradiation (PCI) has been widely adopted as standard of care to reduce the incidence of brain metastases in limited stage SCLC patients who have had a response of their thoracic disease to definitive chemoradiation. PCI has been demonstrated to reduce the incidence of brain metastases (relative risk 0.56; 95% CI, 0.38-0.57) and portends a 5.4% improvement in survival at three years [5].

However, the role of PCI in ES-SCLC patients who have a good response to initial systemic therapy remains unclear. To date, there have been two randomized multicenter trials which evaluated PCI in ES-SCLC. An EORTC phase III trial by Slotman et al., randomized ES-SCLC patients with a response to chemotherapy to either PCI or observation. The primary end point for this study was symptomatic brain metastases. Of note, intracranial screening by MRI was not utilized prior to PCI. When compared to observation, PCI was associated with a lower risk of symptomatic brain metastases (hazard ratio [HR], 0.27; 95% confidence interval [CI], 0.16 to 0.44; $P < 0.001$), higher median disease-free survival (14.7 weeks vs 12.0 weeks), and higher median overall survival (6.7 months vs 5.4 months). The cumulative risk of brain metastases within 1 year was 14.6% in the irradiation group (95% CI, 8.3 to 20.9) vs 40.4% in the control group (95% CI, 32.1 to 48.6), and the 1-year survival rate was 27.1% (95% CI, 19.4 to 35.5) in the irradiation group vs 13.3% (95% CI, 8.1 to 19.9) in the control group [6].

Another phase III trial was performed in Japan, in which ES-SCLC patients with some response to initial chemotherapy were randomized to either PCI or observation. Unlike the EORTC trial, this trial required MRI screening prior to randomization. Preliminary interim analysis, presented at the American Society of Clinical Oncology annual meeting in 2014, demonstrated a trend towards worse overall survival with PCI (10.1 months vs 15.1 months, HR 1.38; 95% CI, 0.95 to 2.01; stratified log-rank test, $p = 0.091$). Compared to observation, PCI significantly reduced the risk of brain metastases (32.4% vs 58.0% at 12 months; Gray's test, $p < 0.001$) and had comparable PFS (median, 2.2 vs 2.4 months; HR 1.12; 95% CI, 0.82 to 1.54) [7].

Both the EORTC and Japanese trials confirm the impact of PCI on reducing the incidence of brain metastases in ES-SCLC patients. However, these trials provide conflicting data on whether PCI provides a survival benefit. Moreover, PCI adversely affects short term quality of life with side effects such as fatigue and hair loss [6]. In addition, there is concern for long-term radiation-induced neurological morbidity [8], [9]. As treatment for ES-SCLC becomes more successful, efforts to minimize neurotoxicity from PCI will be of paramount importance.

b) Tumor Treating Fields (TTFields) Overview

TTFields are a non-invasive, regional antimetabolic treatment modality with minimal toxicity which have been approved for the treatment of recurrent and newly diagnosed glioblastoma (GBM) by the Food and Drug Administration (FDA) in the United States and have obtained a CE mark in Europe for the same indications. TTFields act by delivering low intensity (1-3 V/cm), intermediate frequency (100-300 kHz), alternating electric fields to the tumor using non-invasive transducer arrays placed on the skin around the region of the body containing the tumor. TTFields act predominantly during two phases of mitosis: 1) during metaphase, by disrupting the formation of the mitotic spindle, and 2) during cytokinesis, by dielectrophoretic dislocation of intracellular constituents resulting in apoptosis [10], [11]. The efficacy of TTFields is frequency dependent on specific cell types. The anti-mitotic effect of TTFields has been shown in multiple cell lines when the appropriate frequency was utilized. This includes primary brain tumor cell lines and cell lines from other tumors which commonly metastasize to the brain (glioblastoma at 200 kHz [12], NSCLC at 150kHz [13], breast carcinoma at 120kHz [14], and melanoma at 100kHz [10]). For SCLC, maximal cell death has been found to occur at 200 kHz [15].

The effect of TTFIELDS is directional, *i.e.*, TTFIELDS are most effective when applied in the direction of the division axis of the dividing cell [10], [12]. In order to increase the efficacy of TTFIELDS, two sequential field directions can be applied to tumors by using two perpendicular pairs of transducer arrays. Using two directional TTFIELDS in pilot clinical testing demonstrated TTFIELDS to be biologically active in human tumors. In a pilot trial [16], TTFIELDS were shown to decrease the size of skin metastases from breast cancer and from malignant melanoma. In addition, in a phase I/II trial in 42 pretreated advanced NSCLC patients TTFIELDS were applied to the chest and upper abdomen together with systemic pemetrexed [17]. This trial demonstrated that TTFIELDS therapy were well tolerated by NSCLC patients without any detectable increase in systemic toxicity due to pemetrexed. Interestingly, patients in this trial showed promising local disease control in the lungs and median survival time when compared to historical data in advanced NSCLC with pemetrexed alone. In addition, a phase III trial of TTFIELDS as monotherapy compared to active chemotherapy in recurrent glioblastoma patients [18] showed Optune™ to be equivalent to active chemotherapy in extending survival, associated with minimal toxicity, good quality of life, and activity within the brain (14% response rate). Finally, a phase III trial of Optune™ combined with maintenance temozolomide compared to maintenance temozolomide alone has shown that that combined therapy led to a significant improvement in both PFS and OS in patients with newly diagnosed GBM [19], without the addition of high grade toxicity and without decline in quality of life.

c) Metastasis Prevention Using TTFIELDS

In addition to the impact on the primary tumor, TTFIELDS have been tested for their potential to inhibit metastatic spread of solid tumors to the lungs in two animal models [20]: (1) Mice injected with malignant melanoma cells (B16F10) into the tail vein, (2) New Zealand white rabbits implanted with VX-2 tumors within the kidney capsule. The mice and rabbits were treated using two-directional TTFIELDS at 100–200 kHz. Animals were either monitored for survival, or sacrificed for pathological and histological analysis of the lungs. The total number of lung surface metastases and the absolute weight of the lungs were both significantly lower in TTFIELDS treated mice than in sham control mice ($p < 0.05$). TTFIELDS treated rabbits survived significantly longer than sham control animals. This extension in survival was found to be due to an inhibition of metastatic spread, seeding or growth in the lungs of TTFIELDS treated rabbits compared to controls. Histologically, extensive peri- and intra-tumoral immune cell infiltration were seen in TTFIELDS treated rabbits only (Figure 1).

Rabbits with VX2 Tumors in the Kidney

Mice with Melanoma Injected into the Tail Vein

[figure not shown]

Fig. 1

Right Panel Malignant melanoma metastases as seen on the surface of the lungs of mice treated with TTFields. Exemplary photos of lungs of mice treated with TTFields (A) or sham control (B) are shown after removal of the pulmonary blood by perfusion with saline. Average number of surface metastases (\pm SD) in treated and control mice (C). Average lung weight (\pm SD) of treated and control mice (D)

Left Panel Exemplary photos of surface lung metastases in TTFields treated (A) versus sham control rabbits (B). Treatment was initiated on day 12 from implantation of the kidney tumor. The average total number (\pm SD) of surface metastases (C) and the average number of large metastases (\pm SD) (D) in control versus treated rabbits

d) Clinical Results with Optune™ in Glioblastoma

Based on promising pilot data in both recurrent and newly diagnosed glioblastoma, a phase III trial was conducted in the United States and Europe to test the safety and efficacy of 200 kHz TTFields alone versus active chemotherapy in patients with recurrent glioblastoma [18]. The primary endpoint was overall survival. Patients (median age 54 years (range 23-80), Karnofsky performance status 80% (range 50-100)) were randomized to 200 kHz TTFields alone (n = 120) or active chemotherapy control (n = 117). Active chemotherapy control arm included “physician choice” chemotherapy that predominantly included bevacizumab based regimens, irinotecan or nitrosurea. The median number of prior treatments was 2 (range 1-6).

Median overall survival was 6.6 vs 6.0 months (HR 0.86; 95% CI, 0.66 to 1.12; p = 0.27), 1-year survival rate was 20% and 20% and progression-free survival rate at 6 months was 21.4% and 15.1% (p = 0.13), respectively in TTFields versus chemotherapy treated patients. Responses were more frequent in the TTFields arm (14% vs 9.6%, p = 0.19). The most common TTFields-related adverse event was mild (14%) to moderate (2%) skin irritation beneath the transducer arrays, which was again expected with use of the transducer arrays. These adverse events were effectively treated with topical hydrocortisone. Patients receiving chemotherapy had significantly more gastrointestinal, hematological and infectious complications. Quality of life analyses favored TTFields in most domains. Specifically, cognitive and emotional function were reported to be much better in the TTFields treated patients than with chemotherapy.

The results of this phase III trial demonstrated comparable efficacy with this chemotherapy-free treatment (200 kHz TTFields) to chemotherapy (including bevacizumab) in recurrent glioblastoma with a

more favorable safety profile and quality of life and supported FDA approval of TTFields in recurrent glioblastoma in 2011 and a CE mark in Europe.

Registry data from 457 recurrent GBM patients who started Optune™ prescribed by the treating physician in the US between October 2011 and November 2013 showed an even higher median overall survival of 9.6 months, with baseline characteristics similar to those of patients treated under the pivotal clinical trial [21], [22]. The 2-year survival rate in this population was 30% (compared to 9% in Optune™-treated patients on the clinical trial). Compliance was a clear predictor of survival on Optune™, and patients treated with the device for at least 18 hours per day had significantly longer survival time. No new safety signals have been detected in this registry dataset and the only common adverse event related to Optune™ was skin reaction.

Based on this clinical data in recurrent GBM and a pilot trial in newly diagnosed GBM with Optune™ in combination with temozolomide that demonstrated favorable safety profile and promising efficacy, an international phase III trial in newly diagnosed GBM, evaluating the role of Optune™ in combination with temozolomide maintenance after surgery and chemoradiation versus temozolomide alone was conducted. In the final analysis (n = 695), progression-free survival was 7.1 months for Optune™/temozolomide vs 4.2 months for temozolomide alone (HR 0.694; 95% CI, 0.558 to 0.863; log rank p = 0.0010) and overall survival was 19.4 months for Optune™/temozolomide vs 16.6 months for temozolomide alone (HR 0.754; 95% CI, 0.595 to 0.955; p = 0.0229). This translates into 2-year survival rates of 43% (95% CI, 36 to 50) vs 29% (95% CI, 21 to 38). No significant added toxicity was seen in the temozolomide /Optune™ arm. Quality of life and gross cognitive function were also comparable in the 2 arms.

Based on the data submitted to FDA from this newly diagnosed GBM study, FDA approved Optune™ in combination with temozolomide for the treatment of adult patients with newly diagnosed GBM on October 5, 2015. In the US, Optune™ with temozolomide is indicated for the treatment of adult patients with newly diagnosed, supratentorial glioblastoma following maximal debulking surgery and completion of radiation therapy together with concomitant standard of care chemotherapy.

e) Rationale for Conducting the Clinical Investigation

TTFields are a novel, non-invasive regional anti-mitotic treatment modality. Pre-clinical studies and clinical data in glioblastoma have demonstrated a favorable safety profile and clinical superiority when treating the brain with TTFields. In addition, durable responses have been demonstrated with 200 kHz TTFields monotherapy for supratentorial tumors of the brain.

Brain metastases are a common occurrence in patients diagnosed with SCLC. PCI has been showed to improve survival in patients with LS-SCLC and potentially in patients with ES-SCLC as well. However, it has detrimental effects on quality-of-life, requiring the investigation of alternative strategies which allow for intracranial control while minimizing the risk of neurocognitive adverse effects. As such, prophylactic cranial TTFields may allow for sufficient intracranial control. Due to the favorable safety profile seen in recent phase III glioblastoma trials, NovoTTF-200A to the brain may be an appealing alternative to PCI. If TTFs can treat microscopic disease in the brain and prevent the formation of brain metastases with minimal to no late cognitive effects, then this would potentially improve survival and quality of life for patients with small cell lung cancer. Thus, the safety and efficacy of prophylactic cranial TTF in SCLC patients should be studied.

We hypothesize that prophylactic cranial TTF for patients with ES-SCLC with no evidence of brain metastases will be well tolerated. We anticipate that at least 75% of patients will tolerate treatment for 6 months or greater.

If the safety and tolerability of TTF is achieved, then a phase 2 study will be considered to test the efficacy. The ultimate goal would be for TTF to replace PCI as a safe and efficacious treatment modality to prevent brain metastasis in ES-SCLC. A second potential step would be for this modality to be tested in limited stage SCLC patients.

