6. DESIGN OF THE CLINICAL INVESTIGATION

1. General

a) Description of the Type of Clinical Investigation to be Performed

This is a prospective, single-arm, open-label multicenter pilot study. All patients will undergo TTFs using the NovoTTF-200A System set to an output frequency of 200 kHz. Patients on the study may receive chest irradiation at the discretion of the treating physician. Moreover, should the patient develop progressive extracranial disease, then the patient may receive systemic therapy at the discretion of the treating physician. All oncology therapies will be recorded in the clinical trial record.

NovoTTF-200A will be discontinued in patients who develop intracranial failure while on therapy. All patients who develop intracranial failure may undergo WBRT or best supportive care at the discretion of the treating physician.

All study follow-up procedures should continue according to the study's protocol until death, or until one of the other criteria for removal from the study is met (see **Section 3.C** below).

b) Outcome Measures

Primary Outcome Measure:

Feasibility, as measured by tolerability of TTFs, will be recorded as percentage of patients continuing TTF therapy until intracranial tumor progression, discontinuation due to DLT, or continuation of therapy for at least 6 months.

Secondary Outcome Measures:

1. Time to intracranial failure, as measured from date of starting NovoTTF-200A to intracranial failure as a first event. Death prior to evidence of intracranial failure is treated as a competing risk and will be censored on the time to intracranial failure curves.
2. Overall survival, defined from the date of starting NovoTTF-200A to death, or censored at the date of last follow-up.
3. Rate of intracranial failure at 2, 4, 6, 8, 10, 12 months after starting NovoTTF-200A
4. Intracranial failure free survival, defined from the date of starting NovoTTF-200A to the first intracranial failure or death (whichever occurs first) or, otherwise, censored at the last MRI imaging assessment date on which the patient was reported alive without intracranial failure.
5. Rate of decline in cognitive function as measured by HVLT-R free recall, delayed recall, and delayed recognition; COWAT; and TMT Parts A and B at 2, 4, 6, 8, 10, 12 months follow-up.
6. Time to neurocognitive failure, as measured by cognitive decline on a battery of tests: HVLT-R free recall, delayed recall, and delayed recognition; COWAT; and TMT Parts A and B.

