9. STATISTICAL CONSIDERATIONS

a) Study Endpoints

The primary endpoint is feasibility, measured as percentage of patients continuing TTF therapy until

intracranial tumor progression, discontinuation due to DLT, or 6 months. Death prior to evidence of intracranial failure is treated as a competing risk and the patient is censored at time of death. Death will not be considered as an event and patients who have not had intracranial failure will be censored at the time of death.

Secondary endpoints include:

- Time to intracranial failure, as measured from date of starting NovoTTF-200A to intracranial failure as a first event. Death prior to evidence of intracranial failure is treated as a competing risk and will be censored on the time to intracranial failure curves.
 - Intracranial Failure will be diagnosed based on ONE of the following criteria:
 - New lesion seen on two consecutive axial slices
 - New lesion seen on at least one slice in two separate planes
 - MRI used to diagnose intracranial failure must meet requirements mentioned in inclusion criteria, specifically, the MRI must be a high resolution, isovolumetric T1-weighted post-gadolinium MRI of the brain using a 3T MR scanner. Additional parameters include:
 - FOV: 256 mm x 256 mm
 - Matrix: 256x256
 - Slice thickness: 1 mm
 - Full brain Coverage
 - A lesion is designated “Undetermined” as long as it does not comply with the definition of intracranial failure above. If on a subsequent scan or on an additional imaging modality it is deemed as intracranial failure according to the criteria above, the date of intracranial failure diagnosis will be documented as the first time a new lesion was evident on a scan (i.e., backdated).
- Overall survival, defined from the date of starting NovoTTF-200A to death due to any causes, or censored at the date of last follow-up.
- Rate of intracranial failure at 2, 4, 6, 8, 10, 12 month after starting NovoTTF-200A
- Intracranial failure free survival, defined from the date of starting NovoTTF-200A to the first intracranial failure or death (whichever occurs first) or, otherwise, censored at the last MRI imaging assessment date on which the patient was reported alive without intracranial failure.
- Rate of decline in cognitive function as measured by HVLT-R free recall, delayed recall, and delayed recognition; COWAT; and TMT Parts A and B at 2, 4, 6, 8, 10, 12 months follow-up.

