NCCTG N0574, NCCTG N0577, RTOG 0825, ECOG E3F05, NCCTG N0874/ABTC 09-0, and N107C. Assessments will be conducted every 8 weeks for the first year or until intracranial failure, whichever occurs first. The HVLt-R test has been used and validated in multiple prior phase III trials of patients with brain metastases [9, 21]. HVLt-R incorporates 6 different forms, helping to mitigate practice effects of repeated administrations. Each form includes 12 nouns (targets) with 4 words drawn from 3 semantic categories, which differ across the 6 forms. The test involves memorizing a list of 12 targets for 3 consecutive trials (immediate recall), recalling the 12 targets after a 20-minute delay (delayed recall), and identifying the 12 targets from a list of semantically related or unrelated items (delayed recognition). In COWAT [Johnson SC et al, *Clin Neuropsychol.* 2012; 26(7):1230-41, Johnson DR et al, *Neuro Oncol.* 2012;14(6):808-16], the patient produces as many words as possible in 1 minute for a specific letter and the test assesses language and executive/frontal skills. The test is widely used and is part of the Halstead-Reitan Neuropsychological Battery. Impairment in the understanding of language or the motor expression of language will impair the results in this trial. Since such functions are affected by brain-directed therapies such as WBRT, the test could be sensitive to the experimental treatment effects on those functions. TMT [Bowie CR and Harvery PD, *Nat Protoc.* 2006; 1(5):2277-81] is a measure of visuospatial scanning, attention, sequencing and cognitive processing speed (Part A) and executive function (Part B). Those neurocognitive functions could be affected both by brain metastasis and by therapies directed to the brain, and will therefore be used in the trial. Patients must “connect the dots” either in a numbered sequence or alternating letters and numbers.

b) Sample Size Determination: Because the primary endpoint is feasibility, the proposed sample size is not driven by statistical hypotheses. Rather, we propose the sample size of 25 so that we will have precise enough information for planning the next phase of treatment development. The following table summarizes the point estimate and 95% confidence interval when n=25.

# patients continuing therapy	10	15	18	20
Point estimate	40%	60%	72%	80%
95% confidence interval	23% - 59%	41% - 77%	52% - 86%	61% - 91%

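### The 75% anticipated to tolerate 6 months is on a different scale from the primary endpoint, which also credits patients whose device stops early for intracranial failure

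*Combined protocol and SAP*

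**What the plan says.** Section 3(e) gives one expected figure for tolerability: "We anticipate that at least 75% of patients will tolerate treatment for 6 months or greater". The paragraph after it adds: "If the safety and tolerability of TTF is achieved, then a phase 2 study will be considered to test the efficacy". 'Tolerate' is not defined.

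Section 6, item 1(b), takes tolerability as the measure of feasibility and defines the primary outcome as the "percentage of patients continuing TTF therapy until intracranial tumor progression, discontinuation due to DLT, or continuation of therapy for at least 6 months". The synopsis and Sections 5(a) and 9(a) give the same three end points. Section 6, item 1(a), says that "NovoTTF-200A will be discontinued in patients who develop intracranial failure while on therapy", and the treatment-duration paragraph of Section 6 also ends treatment at death.

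On deaths, Section 9(a) says of the primary endpoint: "Death will not be considered as an event and patients who have not had intracranial failure will be censored at the time of death". Section 9(c) then analyses a single proportion by Wilson's method with a one-sided 95% interval. Section 9(b) says "the proposed sample size is not driven by statistical hypotheses" and tabulates intervals for illustrative rates of 40% to 80%. Section 9 does not mention 75%.

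**The concern.** A patient whose device is stopped at week 8 for a new brain lesion meets the primary endpoint but has shown 8 weeks of tolerance, not 6 months. At a fixed level of tolerance, more early intracranial failure pushes the headline rate up, because a patient who fails early has less time in which to stop for intolerance. That is an awkward property in a trial whose stated hypothesis is fewer brain metastases.

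Two further features blur the rate. The list of end points includes discontinuation due to DLT, so on a literal reading a stop for toxicity counts as continuing. And a simple proportion has no censoring, so it is undefined whether a patient who dies before 6 months is in the numerator, in the denominator only, or in neither.

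At stake is what the pilot can say about tolerability when a phase 2 study is considered. One data set could be presented as well above 75% or well below it, and the choice would be open after the results are known.

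**Working it through.** **The plan's own figures.** The table in Section 9(b) is reproduced by the two-sided 95% Wilson interval, (p + z²/2n ± z√(p(1−p)/n + z²/4n²)) / (1 + z²/n), with n = 25 and z = 1.96: 10/25 gives 23.4–59.3%, 15/25 gives 40.7–76.6%, 18/25 gives 52.4–85.7%, 20/25 gives 60.9–91.1%. All match after rounding. The 75% has no derivation to reproduce.

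**One data set, two scales (illustrative counts).** Of 25 patients, 12 reach 6 months, 9 have intracranial failure earlier and 4 stop for other reasons.
- Primary endpoint: (12 + 9)/25 = 84%, one-sided 95% Wilson lower bound 68.8%.
- Six months on the device: 12/25 = 48%, lower bound 32.6%.
- If the 4 other stops were DLTs, the literal endpoint would be 25/25.

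**Dependence on intracranial failure.** Assume constant, independent hazards and no deaths. Let s be the monthly hazard of stopping for intolerance and f that of intracranial failure. Then
- reach 6 months = exp(−6(s+f));
- primary rate = exp(−6(s+f)) + [f/(s+f)]·[1 − exp(−6(s+f))].

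With 70% true 6-month tolerance, s = −ln(0.70)/6 = 0.0594. Section 3(a) gives brain metastases in the Japanese trial (PCI versus observation) as "32.4% vs 58.0% at 12 months".
- No intracranial failure (f = 0): primary 70%, reach 6 months 70%.
- 32.4% at 12 months, f = −ln(0.676)/12 = 0.0326: primary 0.576 + 0.150 = 73%, reach 6 months 58%.
- 58.0% at 12 months, f = −ln(0.42)/12 = 0.0723: primary 0.454 + 0.300 = 75%, reach 6 months 45%.

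Tolerance is 70% throughout; only the rate of brain metastases changes. In the last case the cumulative incidence of stopping for intolerance is 1 − 0.754 = 25%, so its complement equals the primary rate. A Kaplan-Meier estimate with intracranial failure censored would recover 70%, given independence.

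**Adding deaths.** Take a hazard of death without metastases of 0.010 to 0.046 per month (assumed; the upper value is ln 2/15.1) and re-solve f so that the 12-month cumulative incidence stays at 58%. The share reaching 6 months falls to 41–28%. At the upper value, 28.4% reach 6 months, 35.6% have intracranial failure, 15.7% die and 20.3% stop. The primary rate is then:
- 28.4 + 35.6 = 64% if deaths stay in the denominator only;
- 64.0/84.3 = 76% if deaths are dropped;
- 64.0 + 15.7 = 80% if deaths count as continuing.

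**The 75% read as still on the device at 6 months.** Even with no intolerance, this share cannot exceed the share alive and free of intracranial failure. The documents give 12-month brain-metastasis rates and median survival, not 6-month values, so the latter are assumptions. Under constant hazards, alive at 6 months = 0.5^(6/median) and metastasis-free at 6 months = √(1 − 12-month rate). The range for both together runs from competing hazards fitted to the 12-month incidence up to the simple product. The last column is the product with Weibull shapes 0.75 to 2.

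| Cited arm | Metastases, 12 mo | Median survival | Alive, 6 mo | Metastasis-free, 6 mo | Both, constant hazards | Both, Weibull |
|---|---|---|---|---|---|---|
| Japanese, observation | 58.0% | 15.1 mo | 76% | 65% | 41–49% | 42–72% |
| Japanese, PCI | 32.4% | 10.1 mo | 66% | 82% | 49–55% | 50–71% |
| EORTC, control | 40.4% | 5.4 mo | 46% | 77% | 26–36% | 35–37% |
| EORTC, PCI | 14.6% | 6.7 mo | 54% | 92% | 47–50% | 48–55% |

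Under constant hazards, the chance of observing at least 19/25 (the smallest count at or above 75%) is at most 2.3% in any arm. At shape 2 it is 43% and 38% in the two Japanese arms. These columns lean low, because overall survival includes deaths after metastasis. The loosest ceiling, the smaller of the two 6-month shares, is 65%, 66%, 46% and 54% under constant hazards, but reaches 81% and 78% in the Japanese arms at shape 2. A mix of the best figures across trials (14.6% and 15.1 months) gives 68–70% at constant hazards and 80–86% at shapes 1.5 to 2.

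**The case against.** The documents do connect tolerability with the primary endpoint: the synopsis and Section 6, item 1(b), name tolerability as what it measures. Not counting a protocol-mandated stop at intracranial failure as intolerance is a defensible choice. Early failures will also be visible elsewhere, since the rates at 2, 4 and 6 months and intracranial failure-free survival are secondary endpoints. In the constant-hazard example without deaths, the headline exceeds true tolerance by about 5 points, or 1 to 2 patients of 25, well inside the Wilson interval. All of this stands, and it limits the weight of the point. It does not supply a 6-month tolerance estimate, nor settle how DLT stops and deaths are counted.

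A reader might infer that 75% is out of reach on the protocol's own figures. The documents do not support that. It needs 'tolerate' to mean still on the device, whereas the sentence just before the 75% speaks of treatment being well tolerated. If it means not stopping for intolerance, the cited toxicity (2% grade 3 skin reactions, Section 16) does not make 75% unattainable. The 6-month rates are assumed and come from PCI or observation arms, not TTFields. The EORTC trial had no MRI screening, while this trial excludes brain metastases on MRI. Some assumptions exceed 75%.

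A reader might also take 75% as a go/no-go rule. It is worded as an anticipation, phase 2 will only be considered, and Section 9 plans estimation without a hypothesis.

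**Conclusion.** The 75% in Section 3(e) and the primary proportion are on different scales, and this follows from the text without modelling. The headline rate credits intracranial failure at any time, read literally credits DLT discontinuation, and leaves deaths undefined.

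The gap between the headline and 6-month persistence can be large: 84% against 48% in the illustrative counts, 75% against 45% in the constant-hazard example. The second pair assumes 70% true tolerance, 58% brain metastases at 12 months, independence and no deaths. With deaths at the upper assumed hazard, the counting rule alone moves the headline between 64% and 80%.

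Read as still on the device at 6 months, 75% is unlikely on the cited arms, but not impossible. Read as not stopping for intolerance, it is attainable, but the primary proportion does not estimate it. The result is a cheap improvement in what an estimation-only pilot of 25 can conclude. It is not an error that must be corrected before the trial can proceed.

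**What to change.** 1. In Section 3(e), say which scale the 75% refers to (on the device at 6 months, or not stopped for intolerance by 6 months), and that it is an expectation and not a decision rule.
2. In Section 9(c), report the primary result by route for all treated patients: reached 6 months; intracranial failure before 6 months; DLT discontinuation; death before 6 months; other stop. State which routes enter the numerator and the denominator, and do not count a DLT stop as tolerated. DLT is spelled out in the abbreviation list but not defined, so the split also needs a definition.
3. Add a 6-month estimate of device discontinuation for reasons other than intracranial failure or death. Use cumulative incidence with those two as competing events, in line with Section 9(d), and as a supplement Kaplan-Meier with them censored, each with a one-sided 95% bound. If 'tolerate' means not stopping for intolerance, compare the Kaplan-Meier value with the 75% and state its independence assumption.

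The cost is some wording and a little more analysis, from data already collected; no extra patients or visits are needed. The downside is a 6-month persistence figure that will look less favourable than the headline rate. The wording should be settled before results are seen.
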